Several pieces of equipment and outcome instruments will be utilized in this study. SmartCuffs (Smart Tools Plus, LLC, Cleveland, OH) Blood Flow Restriction Cuffs will be the primary piece of equipment used to complete the intervention portion of this study. The SmartCuff has a Personalized Pressure feature built into it. This feature allows for a personalized pressure calculation based on the patient's limb dimensions and blood flow. With the built-in pressure sensor and on-board computer, it will calculate and set the optimal pressure needed without the need for an external doppler probe or hand pump used by the PT. All study locations utilize this automated BFR cuff. Staff will be trained and/or retrained to ensure consistent practice across sites.

To obtain objective strength measures across the patient's treatment duration, isometric handheld dynamometry using a Mark-10 force gauge, model M3-500 (max capacity of 500 lb force/250 kg force/2500 newton force), will be completed by named investigators at initial evaluation, at 4-weeks, and at either the 9-week or discharge evaluation, whichever is first.

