Several subjective outcome measures will be utilized throughout the study. Function specific subjective outcome measures include: Lower Extremity Functional Scale (LEFS), Knee Injury and Osteoarthritis Outcome Score for patellofemoral pain and osteoarthritis (KOOS-PF), the Tenger Activity Scale, and the Single Assessment Numerical Evaluation (SANE). Pain levels will also be assessed utilizing the Numerical Rating Scale (NRS) Pain Scale, 1-10. The LEFS is a validated 20-question PROM survey used for the measurement of lower extremity function based on the patients' initial function, ongoing progress, and long-term outcome. The KOOS-PF is an 11-question survey that is used to assess five outcomes; they include knee related quality of life, activities of daily living, sport and recreation function, activities, and pain and symptoms. The SANE is a single-item question used globally to assess function. The Numeric Rating Scale is one question pain intensity scale that assesses pain level on a 1-10 scale. The Fear Avoidance Beliefs Questionnaire (FABQ) is a 16 question likert scale questionnaire aimed at assessing how everyday activities assess the patient's current level of pain. The Tenger Activity Scale determines the level of activity prior and post injury. It will be collected at evaluation, 6 months and 12 months. The dynamometry, LEFS, SANE, NRS and KOOS-PF are documented during the initial evaluation, 4-week, and 9-week or at the end of PT. The PROs will be completed at evaluation, 4-week, 9-week or at the end of PT, as well as with a 6 month and 12 month follow-up. See attachment for chart.

Activity	Enrollment	Baseline	4-week	9-week or end of PT	6 months	12 months
Assessed for eligibility			X			
Demographics/baseline activity level			X			
Randomization			X			
Group allocation			X			
PT session			X			
Intervention Group only BFR w/PT	X		X	X		X
Control Group sham BFR w/PT	X		X	X		X
PROs	X	X	X	X	X	X

Subject identification, recruitment, and pre-assessments:

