3. 30% of established 1RM will be utilized for all exercises, each with 4 sets performed to failure (with pain </= 3 or 4/10)
4. One group will utilize BFR between 40-80% occlusion, and the sham group will use a non-inflated BFR cuff.
5. The exercise plan will be a combination of knee dominant, hip dominant, closed chain, and open chain exercises.
6. Different 'phases' of exercise programs performed to failure will be utilized depending on sensitivity levels of each patient. "Exercising to failure" is performing the exercise with the accompanying weights, bands, or body weight as appropriate to the specific exercise with as many repetitions as tolerable to the person with an acceptable pain level. It is determined by the participant, and while they may be encouraged by the therapist, they are not coerced to push beyond their comfort level.

a. Phase 1: (baseline pain > 3 or 4/10 OR weeks 1-4)

- i. Isometric wall squat @ 60 deg knee flexion (for time)
- ii. Romanian Deadlifts (DB or KB)
- iii. Low box step up
- iv. Knee extensions (90-45 deg flexion)

- v. Standing Hip abduction
- b. Phase 2: (Baseline pain <3 or 4/10 OR weeks 5-8)
 - i. Squats to a box (with external weight, height dependent on patient)
 - ii. Romanian Deadlifts (DB or KB or BB)
 - iii. High box step up
 - iv. Knee extensions (full ROM)
 - v. Standing Hip abduction

Individual exercises will progress based on the discretion of the treating physical therapist. A general guideline might include increasing the resistance when sets to failure are >15 repetitions without exceeding a 3 or 4/10 pain during or after each exercise.

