1.2 Data collection and analysis

Along with their standard therapy session reassessments (including routine session notes and progress notes), participants will be asked to complete the PROs at 4-week, 9-week or at the end of PT sessions, 6-month and 12-month intervals. The PROs will be completed by paper and pen while at a therapy session. Baseline, 4-week, and 9-week or end of PT sessions assessments will be completed as part of the routine PT session evaluation process. If the participant is not coming in to Gaylord for appointments, the 6 and 12-month assessments will be completed by phone with the participant or paper copies will be mailed to their last known address. If necessary, an email will be sent to remind them of the study and scheduled assessments.

Information regarding the security of participant's data will be shared with them in the consent form as well as upon request. All information collected specifically for the study will be stored on password protected computers in locked offices. The paper copies of the assessment forms completed as part of routine PT sessions will be stored according to Gaylord procedures in the hard copy of the patient's medical record. Information from the forms will be pulled by study staff and shared across sites only after it is de-identified.

After data is collected and de-identified, it will be analyzed using GraphPad Prism version 9.3.1, or other appropriate statistical software as necessary. Adjustments for abnormal distribution and unequal variance will be applied as necessary. To compare pre- and post-intervention measurements over time on subjective and objective outcome measures, we will use a two-way repeated measures analysis of variance or independent samples t-test to determine the effect of treatment groups (BFR + standard of care therapy and sham + standard therapy). For relationships between variables, we will use correlation and regression analyses as necessary. For categorical data, we will use chi-square testing or Fischer's exact test as necessary. Exact analysis for each test will depend on variance and distribution/normality of data set. We will perform an interim analysis at 50 % participant recruitment in order to assess the effects of the BFR therapy and safety for the subjects, and potential for change in sample size. We will not preclude the possibility of conducting other post-hoc data analyses as appropriate and approved by the IRB.

References

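### The end-of-treatment assessment has no fixed time but is analysed as one time point, so the arm comparison at that visit may be biased, most of all for strength

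*Combined protocol and SAP*

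**What the plan says.** Section 1.1 (Equipment and Instruments) gives two timing rules for the end of treatment.

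- **Dynamometry:** tested at initial evaluation, at 4 weeks, and "at either the 9-week or discharge evaluation, whichever is first".
- **Dynamometry, LEFS, SANE, NRS and KOOS-PF together:** these "are documented during the initial evaluation, 4-week, and 9-week or at the end of PT". The next sentence says "The PROs will be completed at evaluation, 4-week, 9-week or at the end of PT", followed by 6 and 12 months. Neither sentence says which of the two dates applies when they differ.

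The activity chart has a single merged column for 9 weeks or end of therapy. The Study Timeline paragraph lists 9 weeks alone for the PROs. Section 1.2 repeats the either/or wording.

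No discharge criterion, minimum treatment duration or visit window is given. The exercise phases depend on pain or on week (for example "Phase 2: (Baseline pain <3 or 4/10 OR weeks 5-8"), and "Individual exercises will progress based on the discretion of the treating physical therapist". Section 1.1 states that investigators and the assessor are not masked.

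For the analysis, section 1.2 says "we will use a two-way repeated measures analysis of variance or independent samples t-test". It contains no term or sensitivity analysis for the actual time of assessment. No primary outcome or primary time point is named.

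**The concern.** Discharge happens after randomisation and can be influenced by how the participant is doing and by staff who know the allocation. When it sets the date of the outcome, a value from, say, week 5 and a value from week 9 enter the analysis as the same visit. The arms may then be compared at different average times since randomisation. An effect still growing at discharge would also be recorded before its week-9 size, even if both arms leave equally early.

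At stake is the end-of-treatment comparison. For strength, this is the only comparison after week 4. For the PROs it is one of four follow-up comparisons, but with no primary time point named it could still carry the conclusion.

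**Working it through.** **Inputs from section 1.1:** two-sided t-test, alpha 0.05, power 0.80, standardised effect d = 0.635, 40 completers per arm. The outcome and time point behind 0.635 are not stated. **Inputs not in the documents:** recovery rate, discharge times and discharge proportions. Everything that depends on these is assumed.

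**1. The plan's own figure.** The noncentral-t calculation for d = 0.635 gives 39.91 per arm, so 40 per arm and N = 80, with power 0.801. The plan's figure reproduces.

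**2. Illustration: one-week mean timing gap.** Assume linear improvement of G SD over 9 weeks, with BFR measured one week earlier on average. Shift = G / 9; remaining difference = 0.635 − G / 9.

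| Assumed G (SD) | Shift (SD) | Share of 0.635 | Remaining difference | Power, 40 per arm |
|---|---|---|---|---|
| 0.5 | 0.5/9 = 0.06 | 9% | 0.579 | 0.73 |
| 1.0 | 1.0/9 = 0.11 | 17% | 0.524 | 0.64 |
| 1.5 | 1.5/9 = 0.17 | 26% | 0.468 | 0.54 |

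This uses one slope for both arms, which does not fit well with arms that diverge by 0.635 SD. If 1 SD is the sham gain, the BFR slope is 1.635/9 = 0.18 SD per week, the remaining difference is 0.453 and power is 0.52. A one-week mean gap is also not small: if early leavers go three weeks early, it needs a difference in early discharge of 1/3, or 33 percentage points, between arms.

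**3. Early discharge modelled directly.** Let sham gain G and BFR gain G + 0.635 by week 9, both linearly. Proportions pB (BFR) and pS (sham) are measured at week w, the rest at week 9. Expected difference = (G + 0.635)[1 − pB(9 − w)/9] − G[1 − pS(9 − w)/9]. For example, G = 1, w = 5, pB = 0.3 and pS = 0.1 give 1.635 × 0.867 − 1 × 0.956 = 0.46. Ranges below are for G = 0.5 and 1.0 and w = 5 to 7.

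| Discharged early, BFR vs sham | Expected difference (SD) | Power, 40 per arm |
|---|---|---|
| 0% vs 0% | 0.635 | 0.80 |
| 30% vs 30% | 0.55–0.59 | 0.68–0.75 |
| 30% vs 10% | 0.46–0.57 | 0.53–0.71 |
| 50% vs 20% | 0.36–0.53 | 0.36–0.65 |
| 10% vs 30% | 0.64–0.70 | 0.81–0.87 |

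The direction reverses when sham participants leave earlier, and there is no distortion when nobody leaves early.

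**4. No true effect.** With the same discharge rule in both arms, the expected difference is 0 and the type I error stays at 0.05. With unequal discharge proportions (the 30/10, 50/20 and 10/30 rows), the expected difference is G(pS − pB)(9 − w)/9. Its absolute size is 0.02 to 0.13 SD, with rejection rates of 0.051 to 0.091.

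**The case against.** A reader might infer that faster responders will be discharged and measured earlier, and that the difference is therefore biased against BFR. The documents do not support that. They give no discharge rule and predict no difference in discharge time by arm. They also name reasons for leaving that are not recovery, such as a changed diagnosis, pregnancy or a new infection. As steps 3 and 4 show, the distortion can be zero or run either way.

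Three further points stand. The rule that the earlier date governs is written for dynamometry only and should not be read across to the PROs, whose wording is ambiguous. The PROs have scheduled 4-week, 6-month and 12-month assessments and strength has one at 4 weeks, none of which is tied to discharge. And status at the end of care is a legitimate pragmatic target: bias exists only relative to an effect at a fixed 9 weeks, and the plan does not say which of the two it wants.

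What remains is that the plan neither fixes the time nor declares end-of-care status as its target. It then pools values from different times, in a setting where unmasked, discretionary care can influence those times.

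**Conclusion.** The concern holds as a possible bias, not a demonstrated one. The timing statements are inconsistent, the end-of-treatment visit has no fixed date, and the analysis ignores the actual date. Distortion relative to a fixed 9-week effect requires early discharges that depend on response or arm, or an effect still growing at discharge.

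Its size and direction cannot be derived from the documents. The shift of 0.06 to 0.17 SD, with power falling from 0.80 to between 0.73 and 0.54, rests on an assumed one-week gap, linear recovery, a single slope, and 0.635 being the effect at this visit. It shows only that a moderate timing gap would matter in a design with 80% power and nothing in reserve. Strength is the most exposed outcome. The point deserves a change to the plan because a week-9 value that was never collected cannot be recovered at analysis.

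**What to change.** - Reconcile the timing statements in section 1.1 (Study Timeline, Equipment and Instruments, activity chart) and section 1.2.
- Collect the PROs scheduled for this visit from every randomised participant in a fixed window around 9 weeks after randomisation, whether or not discharged, and use that value for the post-treatment comparison. A route already exists: for participants no longer attending, "the 6 and 12-month assessments will be completed by phone with the participant or paper copies will be mailed to their last known address".
- Keep the PRO value at discharge as a secondary record.
- Record the actual assessment date and the mode of collection, and report time to discharge by arm.
- For strength, treat the 4-week test as the comparison unaffected by discharge timing (provided participants are still in therapy then), and label the 9-week or discharge result as end-of-care status. Analysis by actual time should be a sensitivity analysis only: that time may itself be affected by treatment, so modelling it does not remove the bias.

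The cost is protocol wording and one extra phone or mail contact for each participant discharged early. The drawback is that mode of PRO collection will then differ by discharge status, which is why mode should be recorded. No treatment or discharge decision changes.

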1.1 Study design

This study will be a multisite, randomized, sham-comparator controlled clinical trial conducted by Gaylord Specialty Healthcare Physical Therapy, (GSHPT) in Wallingford, Cheshire, Cromwell, Madison, CT, and the University Of Connecticut Health Center (UCHC) in Farmington, CT. All physical therapy related sessions will be conducted at the GSHPT locations listed above. Due to the nature of the intervention, participants and investigators will not be able to be masked to the intervention.

Participants may not know they are in the intervention or sham group and therapists will not confirm or deny their placement. The assessor will not be able to be masked to group assignments, as the presence or absence of certain variables in the dataset, namely the use of BFR inflation, will immediately reveal group assignment.

Sample size:

An *a priori* power analysis for a two-tailed t-test was performed for sample size estimation. With an alpha = .05, power = 0.80, and effect size of 0.635, the projected sample size needed for complete data sets is approximately N = 80. Thus, our proposed sample size of N = 96 will be more than adequate for the main objective of this study, and should also allow for an expected attrition rate of 20%.

Recruitment for this study will remain open until the target N of 80 complete datasets have been collected. This power analysis was performed using data from Dolak's¹ study on PFPS conducted in 2011. Sample size and protocol was also influenced by Brightwell's study on BFR after patellar instability².

Study Timeline:

Participants will be enrolled in the study for approximately 1 year. Starting with their evaluation and consent at the beginning of their therapy sessions, they will complete prescribed therapy and continue to complete PROs within 4-week, 9-week, 6-month and 12-month intervals. We anticipate the study will take approximately 3 years to complete.

Participants and Settings:

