Consented subjects will be assigned to either the sham-comparator control group or BFR Intervention Group according to a pre-generated randomized assignment sheet. Each randomized assignment sheet will consist of equal control and equal BFR assignments whose order has been randomized using the random list generator at <https://www.random.org/lists/>. We will use blocked randomization to reduce the risk that patients will be assigned to the BFR treatment and sham control groups at unequal frequencies. These blocks will have a size of 6. Co-Investigators at each site will be given a unique list with a number of assignments that is in proportion to the number of subjects expected to be recruited at the site; additional assignment lists will be generated if needed. These co-Investigators will be responsible for communicating group assignments to study therapists delivering the intervention, and for ensuring that randomization and treatment order is maintained. It is expected that if the assignment scheme is not maintained for whatever reason, that they will report the incident to the PI and how it was/or still needs to be rectified. No matter group assignment, all consented subjects will be asked to conduct all assessments. Utilizing a proposed sample size of 96 participants, the study will continue until there are at least 40 participants who complete all study related activities in both the intervention and control groups.

Study protocol:

After being identified as a potential study participant and being consented, participants will be randomly assigned to the sham control or BFR group. All physical therapy sessions will consist of typical, standard

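### Alpha .05 and 80% power are stated for one unidentified t-test, while seven measures are compared between groups with no primary test, order or multiplicity adjustment

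*Combined protocol and SAP*

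**What the plan says.** The sample-size text in section 1.1 reports that an a priori "power analysis for a two-tailed t-test was performed for sample size estimation". Its inputs are given as "With an alpha = .05, power = 0.80, and effect size of 0.635", and it concludes that "the projected sample size needed for complete data sets is approximately N = 80". It calls the enrolment target "more than adequate for the main objective of this study", but does not say which outcome, at which time, that objective concerns.

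Under Equipment and Instruments in section 1.1, the plan states that "Several subjective outcome measures will be utilized throughout the study". The measures listed are LEFS, KOOS-PF, SANE, the NRS for pain, FABQ and an activity scale, in addition to isometric dynamometry. That makes seven. The patient-reported measures have up to four follow-up times: 4 weeks, 9 weeks or end of therapy, 6 months and 12 months. Dynamometry has the first two of these and the activity scale the last two.

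Section 1.2 gives the analysis. "To compare pre- and post-intervention measurements over time on subjective and objective outcome measures", the plan will use either a two-way repeated measures ANOVA or an independent-samples t-test, with the exact choice left to the distribution and variance of the data. The only adjustments mentioned are for non-normality and unequal variance.

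**The concern.** An alpha of .05 and a power of 0.80 are properties of one defined comparison. Here they are stated without saying which comparison they belong to, and the analysis section treats all seven measures alike. On that text, a nominal p-value below .05 on any measure could be presented as the trial's positive result. The 5% error rate would not apply to a conclusion reached that way. Nor could a reader tell afterwards whether the reported result was the one for which the trial was sized.

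**Working it through.** **1. The plan's own figure.** Inputs from the sample-size text: two-sided alpha .05, power 0.80, standardised effect d = 0.635. Allocation is 1:1 ("Each randomized assignment sheet will consist of equal control and equal BFR assignments").

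- Normal approximation: n per arm = 2 × (1.96 + 0.84)² / 0.635² = 2 × 7.84 / 0.403 = 38.9, so 39 per arm and 78 in total.
- Noncentral t: n per arm = 39.9, so 40 per arm and 80 in total. Power at 40 per arm is 0.801.

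The stated N of about 80 is reproduced. It is correct for exactly one comparison.

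**2. How many comparisons the analysis text allows.**

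- One test per measure, for example one group effect from each repeated measures ANOVA: 7.
- A t-test for every measure at every follow-up, on the widest reading of the schedule: LEFS, KOOS-PF, SANE, NRS and FABQ at four times (5 × 4 = 20), dynamometry at two and the activity scale at two. 20 + 2 + 2 = 24.
- The same, but with LEFS, KOOS-PF, SANE and NRS tested only at the first two follow-ups: 4 × 2 + 4 (FABQ) + 2 + 2 = 16.

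**3. Chance of at least one p < .05 when there is no effect on any measure.** For k independent tests this is 1 − 0.95^k:

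- k = 7: 1 − 0.95^7 = 30.2%
- k = 16: 1 − 0.95^16 = 56.0%
- k = 24: 1 − 0.95^24 = 70.8%

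The measures come from the same patients, so the tests are correlated. The documents give no correlations, and the values below are assumptions. Results are from simulation of two-sided z-tests with a common correlation (400,000 draws).

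| Assumed correlation | 7 tests | 24 tests |
|---|---|---|
| 0 | 30.2% | 70.8% |
| 0.3 | 27.0% | 59.4% |
| 0.5 | 23.0% | 45.8% |
| 0.7 | 17.8% | 31.1% |
| 0.8 | 14.8% | 23.8% |
| 0.9 | 11.3% | 16.3% |

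Relative to 5%, seven tests give a factor of 11.3/5 = 2.3 to 30.2/5 = 6.0. Twenty-four tests give 16.3/5 = 3.3 to 70.8/5 = 14.2.

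**4. What it would cost to keep every test confirmatory.** Bonferroni thresholds put back into the same t-test calculation with d = 0.635:

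- 7 tests: alpha = .05/7 = .00714. Power at 40 per arm is 0.53, and 64 per arm (128 complete) would be needed for 80%.
- 24 tests: alpha = .05/24 = .00208. Power is 0.37, and 79 per arm (158 complete) would be needed.

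With one designated test, alpha stays at .05 and the 80 complete data sets still give 80% power.

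**The case against.** Collecting several outcomes is normal, and a list of instruments is not a defect. Section 1.2 names repeated measures ANOVA first, and that method analyses all visits of a measure together. A reader might infer that the plan commits to 24 separate t-tests with an error rate of up to 71%. The documents do not support this: they nowhere say that each measure is t-tested at each visit, and the t-test is only one of two options. The schedule is also open to more than one reading. One sentence lists four of the patient-reported measures only to the end of therapy, the next extends the patient-reported outcomes to 12 months, and FABQ has no schedule of its own. Twenty-four is therefore an upper bound.

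Two further objections have force. Overlapping self-reports on the same knee may be highly correlated, which brings the seven-test figure down to little more than twice 5%. And the text available for review lacks an opening part that may name a primary outcome, so it cannot be inferred that the trial has none. If one is named, a single test of it has a 5% error rate and the other measures are ordinary secondary outcomes.

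These objections reduce the size of the problem but do not remove it. Even one ANOVA per measure leaves seven unranked tests. Wherever a primary outcome may be named, neither the sample-size text nor section 1.2 ties the alpha, the power or the 0.635 to it.

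**Conclusion.** The point stands for the text available. The sample size is sound for one two-tailed t-test, but the outcome and time of that test are not identified, and the analysis section sets no primary test, order or adjustment across seven measures. With one test per measure, the chance of at least one false positive is about 11% to 30%. With 24 tests, the most the text allows on this count, it is about 16% to 71%.

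Both ranges assume no true effect on any measure, each test at .05, and a common correlation between 0.9 and 0, which the documents do not supply. They also assume that any significant result would be taken as evidence of efficacy. They leave out the planned interim analysis at 50% recruitment, which is a separate source of error.

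**What to change.** In section 1.2, name one outcome, at one assessment already in the schedule, with one stated test, as the only confirmatory comparison at .05. The existing assessment at 9 weeks or end of therapy would serve; its timing varies between participants, so the text should say that this assessment is used as defined.

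In the sample-size text, state that the 0.635 effect and N = 80 refer to that outcome. The documents do not show which outcome the 0.635 came from, so the sponsor has to confirm it. If the confirmatory outcome or the type of test differs from the one behind the calculation, the power should be worked out again.

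For the remaining measures and times, either apply a Holm correction or report them as secondary, with confidence intervals and no claim of efficacy.

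The change is to wording only. It needs no new visit, measurement or enrolment. The price is a stricter threshold, or a weaker claim, for the secondary results.

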Those who present one or more of the following Exclusion Criteria will not be eligible for study participation, including:

- Member of a defined vulnerable population, women who are or suspected to be pregnant, prisoners, children under 15, or other protected populations
- Body mass of the leg preventing the cuff from fitting properly
- Radiographic evidence of osteoarthritis (\geq Kellgren-Lawrence Grade 2)
- History of intra-articular injection into either knee within 3 –months
- Uncontrolled or untreated inflammatory disorder
- Acute inflammatory disorder
- Uncontrolled Diabetes and/or peripheral neuropathy, impaired circulation
- Uncontrolled cardiac conditions including uncontrolled hypertension
- Areas of thrombophlebitis, thrombosis
- Distal wounds or pain below the knee that is $>4/10$. This level is self-reported by the patient and is based on the Numeric Pain Rating Scale. Patients are asked to rate their pain level on a 0 to 10 scale with 0 being no pain at all and 10 being the worst pain imaginable. Typically, a pain level of 4 or greater is considered the clinical cutoff for continuation or inclusion in a treatment or activity.
- History of or current rhabdomyolysis
- Prolonged immobilization (>3 months)
- Sickle cell anemia
- Lymphadenectomy
- Varicose veins, or a history of personal or immediate family history (parental or sibling) of deep vein thrombosis
- Current infection at or below the level of cuff placement
- Malignancies in or below the area to be treated
- Other conditions/medications that would interfere with subject safety or data collection in the opinion of the PI
- Subjects with an increased risk of non-response as determined by the therapist
- Once entered in the study, a diagnosis change that affects participation. These diagnoses may be pregnancy, a new infection below the cuff level or one that could not be determined until the patient began and in some cases completed PT. Patients whose insurance will not cover imaging tests until they have completed a PT series are eligible since they are presenting with PFPS and

may be in search of a diagnosis. They and their PT are progressing through the exploratory and exclusionary process and if warranted by the Exclusion Criteria will be removed from the study.

Equipment and Instruments:

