Potential study participants will be identified via initial physical therapy evaluation as demonstrated clinical diagnosis. Clinical diagnosis is determined by an integration of both clinical history and physical exam findings, as well as by excluding other musculoskeletal and medical problems with thorough assessment of clinical history, risk factors, and physical examination. People may come to GSHPT with a diagnosis already in place, or they may be diagnosed by the Physical Therapist conducting the exam. Recruitment for the study will take place at four GSHPT locations: Cheshire, Cromwell, Madison, and Wallingford. Referrals for possible eligible participants for knee pain related physical therapy may be made by the usual outside referral sources. The study recruitment flyer will be shared with some of GSHPT's usual referral sources.

Once a diagnosis is reached, the patient will meet with a member of the study team. If the patient meets all inclusion and exclusion criteria, a study team member will begin the process to obtain informed consent. Consent will occur before any enrollment and treatment procedures are performed.

Subject assignment:

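### One fixed block size of 6 on site-specific lists, with unmasked staff, could let up to a quarter of assignments be known with certainty before consent

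*Combined protocol and SAP*

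**What the plan says.** All of this is in Section 1.1 of the combined protocol and SAP.

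- **Block size (Subject assignment).** "These blocks will have a size of 6". No second size and no random variation is mentioned, and the number stands in the protocol that site staff work from.
- **Ratio (Subject assignment).** "Each randomized assignment sheet will consist of equal control and equal BFR assignments".
- **Lists (Subject assignment).** "Co-Investigators at each site will be given a unique list with a number of assignments", sized to expected recruitment. The recruitment paragraph names the sites: "Recruitment for the study will take place at four GSHPT locations: Cheshire, Cromwell, Madison, and Wallingford".
- **Who learns the assignments.** The opening of Section 1.1 says that "participants and investigators will not be able to be masked to the intervention". Under Subject assignment, "These co-Investigators will be responsible for communicating group assignments to study therapists delivering the intervention". Under Exercise Protocol the arms differ visibly to staff: "One group will utilize BFR between 40-80% occlusion, and the sham group will use a non-inflated BFR cuff".
- **Order of events.** A study team member checks eligibility and obtains consent; assignment follows.
- **Discretion over entry (Exclusion Criteria).** One criterion reads "Subjects with an increased risk of non-response as determined by the therapist". Another turns on the PI's opinion about safety or data collection.

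The plan describes no central release of assignments, no sealed envelopes and no other concealment step.

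**The concern.** In a 3:3 block of known size, once one arm has used its three places the rest of the block is determined. Anyone at the site who knows the size and has followed the earlier assignments can then name the next one before the next patient is approached. Hiding the list would not prevent this, because the knowledge comes from past assignments and the printed block size.

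At stake is selection bias at entry. If enrolment can be timed, encouraged or declined in the light of the next assignment, the arms may differ in prognosis from the start. This trial has little else to fall back on: the assessor is unmasked and most outcomes are patient-reported. Baseline adjustment could correct only the part of such an imbalance that is carried by measured factors.

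**Working it through.** The documents give no figure for predictability, so there is none to reproduce. The check starts from the stated design.

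**Inputs.** Block size 6, equal arms, four recruiting locations and planned N = 96, all from Section 1.1. Equality is stated for each sheet; 3:3 within each block follows from the stated purpose of blocking. Assumptions: even recruitment, so 96 / 4 = 24 per site, and an observer who knows the block size and has seen every earlier assignment at that site.

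**Step 1: certain assignments.** There are C(6,3) = 20 equally likely orders. An assignment is certain once one arm is used up.

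| Position in block | Probability that it is certain | Probability that the best guess is right |
|---|---|---|
| 1 | 0 | 0.5 |
| 2 | 0 | 0.6 |
| 3 | 0 | 0.6 |
| 4 | 2/20 = 0.1 | 0.7 |
| 5 | 8/20 = 0.4 | 0.7 |
| 6 | 1 | 1.0 |
| Sum | 1.5 | 4.1 |

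Certain share: 1.5 / 6 = 25.0%. The closed form for block size 2m, 1/(m + 1), gives 1/4 at m = 3. Over 96 patients in complete blocks: 0.25 × 96 = 24. Per block, one assignment is certain with probability 0.6, two with 0.3 and three with 0.1; 0.6 + 0.6 + 0.3 = 1.5, as above.

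**Step 2: best guess.** 4.1 / 6 = 68.3%, against 50% under simple randomisation.

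**Step 3: sites that stop mid-block.**
- 20 patients: 3 × 1.5 + 0 = 4.5; 4.5 / 20 = 22.5%
- 16 patients: 2 × 1.5 + 0.1 = 3.1; 3.1 / 16 = 19.4%
- 10 patients: 1.5 + 0.1 = 1.6; 1.6 / 10 = 16.0%

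**Step 4: staff who see only some assignments (illustration).** Suppose each earlier assignment is seen independently with probability p and the block position is known. Certainty requires all three assignments of the used-up arm to have been seen, so the share is 0.25 × p³. At p = 0.8 it is 0.25 × 0.512 = 12.8%; at p = 0.5 it is 0.25 × 0.125 = 3.1%.

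**Step 5: randomly varying sizes.** Simulation of 24-patient site lists, with an observer who knows the set of possible sizes and all past assignments and updates by Bayes' rule. Ranges are over repeated runs. The largest imbalance is half the largest block.

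| Block sizes | Certain | Best guess right | Largest within-site imbalance |
|---|---|---|---|
| 6 only (exact) | 25.0% | 68.3% | 3 |
| 4, 6, 8 | 2.2% to 2.5% | 67.3% to 67.4% | 4 |
| 6, 8, 10 | 1.8% to 1.9% | 65.3% to 65.5% | 5 |

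**The case against.** **The 25% is a ceiling.** This stands. It needs complete blocks and an observer who has seen everything. Recruitment runs until 40 participants per arm complete, so sites may well stop mid-block. The documents do not say whether the person taking consent is the list-holder, the treating therapist or someone else, and a therapist may see only their own patients. A reader might infer that any staff member will know a quarter of assignments; the documents support only that some could.

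**Varying the blocks changes little for someone who guesses.** This also stands: 68% becomes about 67%. The gain is the near-removal of certain knowledge.

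**List custody matters more.** This stands and shapes the fix. The plan gives site co-investigators the list and describes no concealment, so a list-holder could read every upcoming assignment whatever the block sizes. A reader might infer that varying the blocks cures the problem by itself; it protects only against staff who do not hold the list.

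**The route into enrolment is inferred.** This stands in part. Non-response is undefined in the exclusion criteria and may mean unreturned questionnaires rather than poor response to treatment. A reader might infer that therapists can exclude by expected treatment response; the text does not settle that. The criterion is discretionary on either meaning, as is the one left to the PI's opinion. Nothing in the documents shows intent or manipulation.

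**Two further inferences go too far.** The documents do not say when the protocol became public, and the point needs only that site staff know the size. Nor is any resulting bias wholly beyond analysis: adjustment can reduce the measured part, but not the unmeasured part.

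**Conclusion.** The point holds as a preventable weakness in the randomisation, not as evidence of bias. With one fixed block size of 6 on site lists and unmasked investigators, staff who have seen every earlier assignment at a site could know up to 25% of assignments before consent and guess 68% correctly. The share is lower at sites that stop mid-block, and lower again for staff who see only part of the sequence. The figures assume 3:3 blocks and that site staff know the block size. The change is worth making because it is cheap and removes nearly all certain knowledge, but it must go with a change in who holds the lists.

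**What to change.** For all lists not yet used:

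1. In Section 1.1 (Subject assignment), replace "These blocks will have a size of 6" with a statement that permuted blocks of randomly varying size will be used. Sizes 4, 6 and 8 are one suitable set; 6, 8 and 10 is another.
2. Keep the sizes out of the site protocol, in a file that the sites do not see.
3. Have the lists held by someone not involved in recruitment, who releases each assignment only after consent and enrolment are recorded.

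**Cost.** An amendment to the Subject assignment text, regenerated lists, and an off-site person to release assignments. The plan already foresees generating further lists if needed. The largest within-site imbalance rises from 3 to 4, or to 5 with sizes 6, 8 and 10. Sample size, visits and treatment are unaffected. Lists already in use cannot be repaired this way, since staff who know the size is 6 cannot unlearn it.
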